10.3.2 Statistical Analyses

In addition to the analyses described subsequently, descriptive statistics will be used during the course of the project as part of data management procedures for monitoring data quality. A brief overview of some of the statistical methods that may be used at the time of analysis, both for descriptive purposes and in more comprehensive analysis of the primary research questions, is summarized in the following sections. It is recognized that these methods may be revised, and additional ones considered, as the details of the specific analyses are developed. Details of the statistical analysis will be outlined in the Data Analysis and Monitoring Plan (DAMP).

Descriptive Analyses

Standard descriptive statistics will be used to describe baseline characteristics and follow-up measures, both overall and within each treatment group. Examination of baseline characteristics will include estimates of the distribution of age, race, and other demographic characteristics, baseline severity based upon pain/discomfort, urgency and frequency, and clinical center. These factors will be examined, both separately for each center, and combined across centers. Summary statistics such as means, medians, and ranges will be produced for all measured variables. Frequencies will be computed for all categorical and ordinal variables. Graphical methods including stem-and-leaf diagrams and boxplots will be used to examine distributions, identify potential influential points, and guide in the choice of transformations if warranted. The balance of baseline measures across the treatment groups will be compared using appropriate 2-sample and k-sample tests including analysis of variance (ANOVA), Wilcoxon and Kruskal-Wallis tests, and Fisher's exact tests.

Analysis of Primary Outcome

The analysis comparing the mean change in NIH-CPSI overall score from 0 to 6 weeks among treatment arms will utilize a linear regression model (equivalent to a 2-way analysis of variance) with a random effect to allow for clustering on clinical center. Standard regression diagnostics will be used to assess model adequacy and examine potential outlying or influential data points. Secondary analyses of the primary endpoint will include multivariable regression models to evaluate whether observed treatment differences, if any, can be partially accounted for by baseline differences in prognostic factors between treatment arms. Profiles of the overall NIH-CPSI score over time will also be compared among treatment groups using random effects regression models (35).

Secondary Analyses

A number of secondary analyses will be conducted, both to evaluate the secondary symptom-related outcomes and to supplement the primary endpoint comparison. Evaluation of some of the secondary outcomes will involve comparison of binary outcomes or response rates among groups. These endpoints may include the global assessment of change, change in white blood cell counts in the four-glass test, subscores of the NIH-CPSI, MOS SF12, and voiding frequency measured by a one day voiding log.

For example, one type of response will be defined based on the participant reported global assessment of change as measured at six (6) weeks or withdrawal, whichever comes first. A seven point scale will be used: 0) markedly worse; 1) moderately worse; 2) slightly worse; 3) no change; 4) slightly improved; 5) moderately improved; and 6) markedly improved. Participants who answer either 5) moderately or 6) markedly improved on this question will be considered to be responders. For this endpoint, participants who withdraw from the study for any reason (e.g. adverse events or participant choice) prior to six (6) weeks will be considered treatment non-responders. Following standard “intent-to-treat” methods, these withdrawals will be included in the denominator of the response rates for evaluation. This outcome will also serve as a validation for the primary endpoint above.

For binary outcomes, analyses comparing response rates will make use of the exact conditional test (ECT) version of Mantel-Haenszel methods to adjust for within-center clustering, as implemented within the Proc-StatXact software system(36). Additional analyses of such endpoints will rely on logistic regression and generalized estimating equation (GEE) methods to evaluate whether observed differences, if any, are attributable to imbalances in prognostic factors such as baseline symptom severity(37). The table below shows required sample sizes for comparison of response rates assuming 80% power to detect the specified difference between groups at a two-sided $\alpha = 0.05$ level of significance using the Fisher’s exact test, with additional sample size adjustments as mentioned above. A baseline response rate of 30% is a typical placebo rate for symptom-related outcomes.

Smaller Response Rate	Larger Response Rate								
	30%	35%	40%	45%	50%	55%	60%	65%	70%
10%	288	204	152	116	96	80	68	56	48
20%	1248	600	364	248	176	140	108	88	72
30%		5648	1500	696	412	272	192	144	112
40%				6272	1620	740	428	276	192
50%						6396	1620	724	412

For the various measures evaluated over time, changes over time will be compared among treatment groups using methods for longitudinal data analysis(35). These methods will include random effects regression models for continuous outcomes and GEE methods for categorical and ordinal outcomes(35). Both within- and between-participant variability in these outcomes will be carefully assessed to provide pilot data for future clinical trials. For measures obtained only at baseline and one follow-up time point, change from baseline will be compared among groups using analysis of variance (ANOVA) and regression methods. When applicable, additional analyses of the symptom outcomes will include evaluation of time to response defined by specific changes in symptoms (e.g. 50% drop in symptom score). Associations between longitudinal changes in secondary outcomes and the overall participant assessment of improvement will be used to supplement the primary endpoint analysis and evaluate the validity of the symptom scales for assessing change.

Withdrawal rates will be compared among arms using standard methods for failure-time data including Kaplan-Meier curves, logrank tests, and Cox proportional hazards modeling(38). In addition, time to response will be compared among groups(38)

Post Treatment Period

Two sets of analyses will be done using post-treatment data (weeks 6-12). First, an analysis of the longitudinal changes in symptoms from 0 – 12 weeks will be done using the methods described above to evaluate durability of response. Secondly, an analysis of the time until need for rescue medication will be done using the survival methods described above. It is recognized that those participants who choose medications at the end of treatment will be considered failures at 6 weeks for this analysis.

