2.3 Study Endpoints

2.3.1 *Primary Endpoint*

The primary endpoint to be used for efficacy evaluation is the overall NIH-CPSI (Appendix A) (scale of 0-43). The change in this score from baseline to six (6) weeks will be calculated for each participant and compared among treatment groups (see Section 10.3 for details of primary endpoint analysis).

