10.2 Sample Size Calculations

The primary endpoint on which sample size estimates are based is the change in the overall NIH-CPSI score from baseline (randomization) to six (6) weeks. The total score has a potential range of 0 – 43 points. For each of the two primary comparisons--ciprofloxacin (CIPRO®) versus no ciprofloxacin (CIPRO®) or tamsulosin hydrochloride (FLOMAX®) versus no tamsulosin hydrochloride (FLOMAX®), we desire adequate numbers of participants to detect a difference of four (4) points in the change from baseline. We require 80% power to detect the specified difference between groups at a two-sided $\alpha = 0.05$ level of significance using a two-sample t-test. After adjustments to allow for possible dilution of statistical power due to interaction in the factorial design (50% increase), withdrawal (15% increase), clustering within Clinical Center (15% increase), a total of 184 participants or $184/4 = 46$ participants per arm will be required. Total required sample sizes for alternative differences are shown in the table below.

Δ	Trial Design	Total Sample Size using sd of change $\sigma = 6.76$
3 points	2 arms	216 (108/arm)
	3 arms	420 (140/arm)
	4 arms	644 (61/arm)
	2 x 2	324 (81/arm)
4 Points	2 arms	122 (61/arm)
	3 arms	237 (79/arm)
	4 arms	368 (92/arm)
	2 x 2	184 (46/arm)
5 Points	2 arms	80 (40/arm)
	3 arms	156 (52/arm)
	4 arms	240 (60/arm)
	2 x 2	120 (30/arm)

In addition, for each individual treatment arm of 46 subjects, the width of a 95% confidence interval for adverse event and other rates will be no wider than $\pm 15.0\%$. It is expected that these 184 participants can be accrued within approximately ten (10) months. Allowing for an additional twelve (12) weeks of follow-up on all participants, the entire study should require fourteen (14) months for completion.

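### The primary analysis of NIH-CPSI change omits the baseline score: valid, but it gives up precision by an amount the protocol does not let one fix

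*Protocol*

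**What the plan says.** Protocol section 2.3.1 defines the endpoint: "The change in this score from baseline to six (6) weeks will be calculated for each participant and compared among treatment groups". Section 10.2 sizes the trial on the same quantity, the "change in the overall NIH-CPSI score from baseline (randomization) to six (6) weeks", with an SD of change of 6.76 and an unadjusted two-sample t-test.

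Section 10.3.2 says that the primary analysis "will utilize a linear regression model (equivalent to a 2-way analysis of variance) with a random effect to allow for clustering on clinical center". A two-way analysis of variance here means the two treatment factors, so the named model is ciprofloxacin, tamsulosin and a random centre effect. Baseline NIH-CPSI is not in it. Adjustment comes one step later: "Secondary analyses of the primary endpoint will include multivariable regression models to evaluate whether observed treatment differences, if any, can be partially accounted for". The explanation to be examined there is imbalance between the arms in prognostic variables at entry.

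The score is collected at both screening visits (sections 7.2 and 7.3, Appendix C). The second is the visit at which randomisation takes place. In its text on binary outcomes, section 10.3.2 itself gives baseline symptom severity as an example of a prognostic factor.

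**The concern.** In a randomised comparison of a score measured before and after treatment, a change score fixes the coefficient of baseline at 1. Regression on baseline estimates that coefficient instead. Unless the true slope of week-6 score on baseline happens to be 1, the change score carries variance that could have been removed with data already in hand.

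Two things are at stake. The standard errors of both primary comparisons may be larger than they need be. And if the arms differ by chance at baseline, part of that difference passes into the primary estimate and is addressed only in a secondary model, run to see whether an observed effect can be explained by it.

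**Working it through.** **1. The protocol's own figure.** Inputs from section 10.2: difference 4 points, SD of change 6.76, two-sided 0.05, 80% power, t-test. The noncentral t gives 46 per group (power 80.2%), or 92 in total. The allowances are 15% for withdrawal, 15% for clustering and 50% for interaction.
- Two arms: 92 × 1.15 × 1.15 = 121.7, rounded to 122.
- 2 × 2 design: 92 × 1.15 × 1.15 × 1.5 = 182.5, rounded up to 184.

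Both match the table, so 184 is consistent with the unadjusted analysis.

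**2. Effect of adjusting for baseline.** Let s be the baseline SD, ks the week-6 SD and r their correlation.
- Variance of change: s²(1 + k² − 2kr).
- Residual variance after adjustment: k²s²(1 − r²).
- Ratio: k²(1 − r²) / (1 + k² − 2kr), which is (1 + r)/2 when k = 1.

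The denominator minus the numerator is (1 − kr)², which is never negative. So the ratio cannot exceed 1, and it reaches 1 only when kr = 1. In finite samples the price is one degree of freedom.

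Neither r nor k is in the protocol. The values below are assumptions, shown as a range.

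| k | r = 0.3 | r = 0.5 | r = 0.7 |
|---|---|---|---|
| 1 | 0.65 | 0.75 | 0.85 |
| 1.25 | 0.78 | 0.89 | 0.98 |
| 1.5 | 0.87 | 0.96 | 0.998 |

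Expressed as extra participants (1/ratio − 1), the gain over r = 0.3 to 0.7 is 54% down to 18% at k = 1, 28% down to 2% at k = 1.25, and 15% down to 0.2% at k = 1.5.

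**3. On the protocol's scale.** With all its allowances the design detects 4 points, and adjustment multiplies this by the square root of the ratio.
- k = 1: 4 × √0.65 = 3.2 to 4 × √0.85 = 3.7.
- k = 1.25: 4 × √0.78 = 3.5 to 4 × √0.98 = 4.0.
- k = 1.5: 4 × √0.87 = 3.7 to 4 × √0.998 = 4.0.

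Put as power for 4 points at the effective 46 per group, k = 1 gives 93.6%, 90.0% and 86.1% at r = 0.3, 0.5 and 0.7, against 80.2% unadjusted.

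**4. Chance imbalance.** The slope of change on baseline is kr − 1. At k = 1, a baseline difference d between the two levels of a factor therefore shifts the change-score estimate by (1 − r)d in size. With SD of change 6.76, the implied baseline SD is 6.76/√(2(1 − r)), or 5.71, 6.76 and 8.73 at r = 0.3, 0.5 and 0.7. Take 184 × 0.85 ≈ 156 evaluable men, before any clustering or interaction allowance. One standard error of d is the baseline SD × √(4/156). The resulting shifts are 0.64, 0.54 and 0.42 points. A two-standard-error imbalance shifts the estimate by about 0.8 to 1.3 points, or 21% to 32% of the 4-point target. Adjustment removes this shift when the relation is linear.

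**The case against.** The strongest reply is that nothing here is wrong. Endpoint, sample size and model all use change from baseline, 184 reproduces, and the type I error is as stated. Change already subtracts baseline, so only the residual slope carries an imbalance through, and the standard error allows for it on average. All of that stands. It limits the point to efficiency and to what happens given a particular imbalance.

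A second reply is that the text is provisional: "It is recognized that these methods may be revised, and additional ones considered, as the details of the specific analyses are developed", with details deferred to the Data Analysis and Monitoring Plan. That plan could add the covariate. But section 10.3.2 is not silent: it names a primary model without baseline and gives adjustment secondary status, so adding it later would depart from the protocol.

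Three stronger readings are tempting, and the protocol does not support them.

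- **That the entry criterion of at least 15 points strengthens the case.** Under a linear relation, selecting on baseline leaves the slope unchanged and shrinks baseline variance, so the baseline/change correlation weakens. For example, with an assumed mean of 22, SD of 8 and r of 0.5 before selection, a simulated cut at 15 moved it from −0.50 to −0.41. A floor at entry and none at week 6 also tends to push k above 1, where the gain is smaller in the range tabulated. The regression to the mean that it causes is common to all arms and does not bias a randomised contrast.
- **That a gain worth at least 18% more participants is assured.** That is the lower end only for equal SDs and r up to 0.7.
- **That the detectable difference falls from about 3.0 points.** The figure 2.80 × 6.76 × √(4/156) = 3.03 leaves out the clustering and interaction allowances of section 10.2. With them the starting point is 4 points.

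**Conclusion.** The point holds as one of lost precision. The primary model leaves out a baseline score that is already collected, at a cost between substantial (variance ratio 0.65 at k = 1, r = 0.3) and negligible (0.998 at k = 1.5, r = 0.7). Under linearity and in large samples, adjustment does not make matters worse. Within a realised trial, a chance baseline imbalance also moves the primary estimate, by (1 − r)d in size if the SDs are equal.

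A reader might infer that the planned test is biased or the trial too small. Neither follows: the unadjusted test is valid, and 184 is adequate on the protocol's inputs. Nor is having a primary and a secondary analysis a defect, since the protocol says which is which. Confidence is high in the direction of the gain and low in its size, because r and k are assumed.

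**What to change.** In section 10.3.2, specify the primary mixed model as change in NIH-CPSI from baseline to six weeks on the two treatment factors, the baseline NIH-CPSI score and a random centre effect. Name the Screening Visit 2 score as the covariate, in line with section 10.2, which takes baseline as randomisation. Keep the unadjusted comparison of change as a sensitivity analysis, and carry the same wording into the Data Analysis and Monitoring Plan.

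With change as the outcome, the endpoint and the 4-point target stay as they are. The cost is about one sentence and one degree of freedom. No new data are needed and the sample size remains 184.

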2.3.2 Secondary Endpoints

A number of secondary outcome measures related to both specific symptoms and overall symptom scores will be used to supplement the analysis based on the primary endpoint. One secondary endpoint will be a participant-reported global response assessment (GRA) at six (6) weeks or withdrawal; whichever comes first, relative to overall baseline symptoms. Additional symptom-related outcome measures include the NIH-CPSI subscales and MOS SF-12.

Laboratory measures to be followed include WBC in EPS. While the true significance of WBC count in the EPS has yet to be established, it nevertheless is the primary marker of intraprostatic inflammation that can be obtained non-invasively. The exact cutoff point for deciding that inflammation is present is also controversial, with most authors relying on 10 WBC per hpf in a wet mount sample. While many investigators have pointed out the variability of WBC count in participants with CPPS over time,(8) fluctuations in the short term, such as for durations contemplated in this study, are less of a problem(9).

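### White-cell counts, measured at baseline and week 6 only, fall under a change-from-baseline comparison with no scale or baseline adjustment named; analysed untransformed and unadjusted, skewed counts would lose power

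*Protocol*

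**What the plan says.** Section 2.3.2 of the protocol makes the count a secondary laboratory measure: "Laboratory measures to be followed include WBC in EPS". It calls this count the main non-invasive marker of inflammation within the prostate, while conceding that its significance is not established.

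Section 7.2 (item 6) and Appendix C place the four-glass test at Screening Visit 1 and week 6 only. The counts therefore come under the rule in Section 10.3.2 for measures with a baseline and a single follow-up: "change from baseline will be compared among groups using analysis of variance (ANOVA) and regression methods".

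The same section lists "change in white blood cell counts in the four-glass test" as a possible endpoint in the paragraph on binary outcomes and response rates. Under Descriptive Analyses it says that graphs will "guide in the choice of transformations if warranted". It describes its methods as open to revision and sends the details to the DAMP, which the opening of Section 10 promises before the study starts.

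**The concern.** Cells per high-power field cannot fall below zero and can be expected to have a long right tail. An untransformed change is then dominated by the few men with very high counts, and a drug that lowers counts by a proportion shows mainly in those men. A change score that is not adjusted for baseline also gives up precision whenever the two visits are less than perfectly correlated. The one rule that governs these counts names the change as the outcome and mentions neither a log or rank scale nor the baseline as a covariate. Cutting the change into responders, which the text also allows, discards further information.

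At stake is the trial's direct laboratory evidence on inflammation. Sections 3.1 and 3.3 raise an anti-inflammatory action of ciprofloxacin as one explanation for any benefit.

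**Working it through.** **Number of men.** The protocol states no power for white-cell counts. Its primary-endpoint size does reproduce, and it supplies the numbers used here. The aim is to "detect a difference of four (4) points in the change from baseline", with SD 6.76, two-sided 0.05 and 80% power. A two-sample t-test needs 46 per group. Then 46 × 1.15 × 1.15 = 60.8, so 61 per group and 122 in all; 122 × 1.5 = 183, rounded up to 184 for four equal arms. Each drug comparison is 92 v 92, and 92 × 0.85 = 78.2, so about 78 v 78 after 15% withdrawal.

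**Loss from the change score alone, without skew.** The change has variance 2σ²(1 − ρ); the baseline-adjusted week-6 value has σ²(1 − ρ²). The efficiency of the change is their inverse ratio, (1 + ρ)/2. When the adjusted analysis has 80% power, the change has Φ(2.802 × √((1 + ρ)/2) − 1.960):
- ρ = 0.3: 62%
- ρ = 0.5: 68%
- ρ = 0.7: 73%
- ρ = 0.9: 78%

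**Simulation at a fixed effect.** All inputs are assumptions except the group size: Poisson counts with log-normal variation between men, mean 8 per field, 40% fall, 78 v 78. Log analyses use log(count + 1). Share lost = 1 − (untransformed change ÷ adjusted log). Repeat runs differ by a few points.

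| SD of log mean | Visit correlation | Untransformed change | Log change | Log, baseline-adjusted | Share lost |
|---|---|---|---|---|---|
| 0.5 | 0.5 | 94% | 98% | 100% | 6% |
| 0.8 | 0.8 | 88% | 96% | 98% | 10% |
| 1.0 | 0.9 | 84% | 94% | 98% | 14% |
| 1.0 | 0.5 | 46% | 70% | 86% | 47% |
| 1.25 | 0.5 | 27% | 52% | 69% | 61% |
| 1.5 | 0.5 | 18% | 38% | 53% | 66% |

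With no effect, the untransformed change, log change and adjusted log analyses rejected in about 4-5% of runs (checked in the same model). If only 50 v 50 men supply EPS (SD 1.0, correlation 0.5), the three powers are about 33%, 52% and 67%.

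**Simulation at a just-detectable effect.** Here the effect is set so that the adjusted log analysis has about 80% power (mean 10 per field, 78 v 78). This removes the ceiling in the first rows above and separates the two sources of loss.

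| SD of log mean | Correlation | Untransformed change | Log change | Untransformed, adjusted | Log, adjusted | Share lost |
|---|---|---|---|---|---|---|
| 0.5 | 0.5 | 60.0% | 66.5% | 84.7% | 83.9% | 28% |
| 0.5 | 0.9 | 73.1% | 71.0% | 85.3% | 80.3% | 9% |
| 0.8 | 0.5 | 50.3% | 68.0% | 74.3% | 82.4% | 39% |
| 0.8 | 0.9 | 73.0% | 76.7% | 83.2% | 83.5% | 13% |
| 1.2 | 0.5 | 31.1% | 61.0% | 56.2% | 77.6% | 60% |
| 1.2 | 0.9 | 50.3% | 71.7% | 63.8% | 77.3% | 35% |

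At SD 0.5, adjusting for baseline recovers the whole loss without a log scale. At SD 1.2 and correlation 0.5, adjustment alone raises 31% to 56%, the log alone raises it to 61%, and both together give 78%. Over all means tried (5, 10 and 20 per field), the loss was 28-63% at SD 1.2 and 6-15% at SD 0.5-0.8 with correlation 0.9.

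**The case against.** The strongest reply is that the protocol does not prescribe an untransformed, unadjusted analysis. The rule does not state a scale, and it names regression as well as ANOVA, which leaves room for a baseline covariate. The section foresees transformations and revision, and the DAMP is due before the study starts. Scale and covariates for a secondary laboratory measure are ordinary analysis-plan content. All of this stands, and it is why the loss is stated conditionally. What remains is that the rule does choose change from baseline as the outcome, and a better outcome and model exist for data already being collected.

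Four stronger readings are tempting but unsupported:
- *A quarter or more of the power is bound to be lost.* The protocol gives no mean, spread or correlation for these counts, and the loss is much smaller in several plausible settings. Section 2.3.2 also says that short-term fluctuation is less of a problem, which leans towards a higher correlation.
- *The scale will be chosen after the data are seen.* The text does not say so, given when the DAMP is promised.
- *A null result would largely reflect the method.* Even the adjusted log analysis misses a 40% fall in 31% of trials at SD 1.25 (100 − 69) and 47% at SD 1.5 (100 − 53), and a 40% effect is itself only an assumption.
- *A responder cut is planned for this outcome.* It is listed only as a possibility, and no cut for change is defined.

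**Conclusion.** The point holds as a conditional one. The stated comparison for white-cell counts is change from baseline, with no scale or baseline adjustment named, and their status as continuous or binary is left open. If the change is analysed untransformed and unadjusted, a baseline-adjusted log-scale analysis was more powerful in every setting simulated.

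For a 40% fall, the loss is about 5-15% of power at moderate skew or high correlation, and about 30-65% at an SD of the log mean near 1.25 or above. Two qualifications apply. The small figure at moderate skew partly reflects power near its ceiling; for a just-detectable effect at correlation 0.5 the loss there is nearer 28%, and it then comes from the missing adjustment rather than from skew. The settings in between (SD 1.0, correlation 0.5) give about 47%.

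All of this rests on an assumed Poisson-lognormal model and a proportional effect. The outcome is secondary and no power is claimed for it, so the priority is low.

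**What to change.** State in Section 10.3.2 or the DAMP, before data are seen, that white-cell counts are analysed as week-6 log(count + 1), adjusted for baseline log(count + 1), both drugs and centre, and reported as ratios of geometric means of (count + 1). Add a rank analysis adjusted for baseline rank as a check, and label any responder cut as supportive only. That also settles whether the outcome is continuous or binary.

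The cost is one sentence, with no extra data or visits. The drawback is that results appear as ratios rather than as differences in cells per field; medians by arm at each visit can be shown alongside to help readers.
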